5.1.3 Trial Plan

A summary of the schedule of study vaccinations and blood samplings for eligible subjects is provided in

Period	Prior to Amendment 1			Post Amendment 1					
Visit	Visit 1	Visit 2	Visit 3	Visit 4	Visit 5	Visit 6	Vis	it 7	Visit 8
Time point	D0	M1	M2	M6	M7 †	M8 †	M12†	M13†	M14†
	Gardasil + CYD			Gardasil + CYD			CYD		
Group 1 *	BL	BL			BL§			BL	
	Gardasil	CYD		Gardasil	CYD			CYD	
Group 2	BL	BL	BL		BL§				BL

Table 5.1: Injection and blood sampling schedule by Group

D: day; M: month; BL: blood sample; CYD: CYD dengue vaccine

* When concomitantly administered, the CYD dengue vaccine and Gardasil will be administered in 2 different sites with the CYD dengue vaccine administered in one deltoid and Gardasil in the other deltoid

§: If the first visit performed after vaccination pause is M7 (Visit 5), both dengue unexposed and dengue exposed subjects who will continue in the study but refuse to receive the next CYD dengue vaccine injection(s) will be proposed to be blood sampled for HPV immunogenicity assessment post Gardasil dose 2.

[†] At the time of Protocol Amendment 1, procedures at M7, M8 and M12 were on hold depending on subjects' progression. Time for the approval of Protocol Amendment 1 by the competent authorities and completion of the associated logistic tasks will result into a delay of study activities of several months (approximately 2 months), and thus to an extension of study duration for dengue exposed subjects.

At the time of Protocol Amendment 1 writing, all subjects except 8 (all from Group 2) have received the second injection of CYD dengue vaccine and all the subjects had completed the vaccination schedule for Gardasil. The next study visits are planned at following time points:

- For Group 1, M7 (Visit 5) or M12 (Visit 7)
- For Group 2, M7 (Visit 5) for the 8 subjects waiting to receive the second CYD dengue injection and M8 (Visit 6) or M13 (Visit 7) for the remaining subjects.

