9.1.1.2 Immunogenicity Assessment Methods

HPV Abs

The competitive Luminex immunoassay for HPV 6, 11, 16 and 18 is performed by Merck & Co. A reference serum, assay controls (phycoerythrin [PE]-tagged type-specific monoclonal antibodies [Mab]) and samples are added to black opaque 96-well microtiter plates. Virus-like particle (VLP)-microspheres for types 6, 11, 16 and 18 are added to each well at 5,000 VLP-microspheres per HPV type. The plates are then covered with foil and incubated for 15 minutes to allow antibodies in the sera to bind to the coated microspheres. Next, type-specific PE-tagged Mab are added to each well and mixed, and then plates are covered with foil and incubated overnight to allow the antibodies in sera samples to compete with the binding of the type-specific PE-tagged Mab. After incubation, all samples are transferred to prewet 96-well filter plates and the serum samples are washed 3 times with phosphate-buffered saline (PBS) and resuspended in PBS plus 1% Bovine Serum Albumin for analysis.

The fluorescent signal from bound HPV-specific, detection monoclonal antibodies (MAbs) is inversely proportional to the patient's neutralizing antibody titer. The correlation of median fluorescent intensity (MFI) units to mili-Merck Units per mL (mMU/mL) is made by serially diluting a reference serum and interpolating the MFI data through a 4-parameter logistic curve fit.

LLOQ values for HPV are 20 mili-Merck Units (mMU)/mL for HPV-6 and HPV-16, 16 mMU/mL for HPV-11, and 24 mMU/mL for HPV-18.

This assay will be performed on samples taken at V01, V02, and V05.

If the first visit performed after vaccination pause is Visit 5, both dengue unexposed and dengue exposed subjects who will continue in the study but refuse to receive the next CYD dengue vaccine injection(s) will be proposed to be blood sampled at this visit for HPV immunogenicity assessment post Gardasil dose 2. While the preferred sample is to be collected 1 month after the second dose of Gardasil, antibody levels are relatively stable from 7 to 12 months after the first dose (or 1 to 5 months after the second dose) (28) (29)

Dengue Neutralizing Abs

Dengue neutralizing Ab levels will be measured by PRNT₅₀ (using parental dengue virus strains of the CYD dengue vaccine constructs) by Sanofi Pasteur GCI, Swiftwater, USA (or outsourced with a GCI selected external laboratory).

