12.2.2 Per-Protocol Analysis Set

Two PPASs will be defined: one for Gardasil (PPG) and one for the CYD dengue vaccine (PPC). The PPASs are subsets of the FAS.

PPG

The subjects presenting with at least one of the following relevant protocol deviations will be excluded from the PPG:

- Subject did not meet all protocol-specified inclusion criteria or met at least one of the protocol-specified exclusion criteria
- Subjects identified as dengue unexposed (seronegative) at baseline
- Subject is seropositive at baseline for Gardasil (i.e., at least one Ab levels against Gardasil HPV antigens > LLOQ at baseline)

- Subject did not complete the vaccination schedule (until V05)
- Subject received a vaccine other than the one that he/she was randomized to receive (until V05 for Group 1, V06 for Group 2)
- Administration of vaccines was not done as per-protocol (site and route of administration) (until V05)
- Subject did not receive vaccines in the proper time window (until V05 for Group 1, V06 for Group 2)
- Subject did not provide after the 2nd dose of Gardasil a post-dose serology sample in the proper time window or a post-dose serology sample was not drawn (until V05 for Group 1, V06 for Group 2)
- Subject received a protocol-prohibited medication (prohibited therapies / medications / vaccines are indicated in Section 6.7) (until V05 for Group 1, V06 for Group 2)
- Subject's serology sample after the 2nd dose of Gardasil did not produce a valid test result, i.e., no Gardasil antigen titer available (until V05 for Group 1, V06 for Group 2)

PPC

The subjects presenting with at least one of the following relevant protocol deviations will be excluded from the PPC:

- Subject did not meet all protocol-specified inclusion criteria or met at least one of the protocol-specified exclusion criteria
- Subjects identified as dengue unexposed (seronegative) at baseline
- Subject did not complete the vaccination schedule
- Subject received a vaccine other than the one that he/she was randomized to receive
- Administration of vaccines was not done as per-protocol (site and route of administration)
- Subject did not receive vaccines in the proper time window
- Subject did not provide after the 3rd dose of the CYD dengue vaccine a post-dose serology sample in the proper time window or a post-dose serology sample was not drawn (V08, M13 for Group 1 and M14 for Group 2)

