‡: Concomitant therapy and ongoing medication will be collected for Days 0–28 after each injection only.

§: Blood samples planned during vaccination visits will be taken before vaccination.

§§: Solicited injection site reactions will be collected for Days 0–7 after each injection. Solicited systemic reactions will be collected for Days 0–14 after each injection. Unsolicited events will be collected for Days 0–28 after each injection. Serious adverse events (SAEs) will be reported throughout the study and AEs of special interest (AESIs) will be collected in defined time windows according to the type of AESI (hypersensitivity/allergic reactions [serious or not] within 7 days after each CYD dengue vaccine injection, serious viscerotropic disease within 30 days after each CYD dengue vaccine injection, serious neurotropic disease within 30 days after each CYD dengue vaccine injection; serious dengue cases requiring hospitalization [i.e., hospitalized suspected dengue case] will be reported during the entire study).

§§§: Termination record will be checked either during a planned study visit or a phone call.

\*\*\*: If the first visit performed after vaccination pause is Visit 5, both dengue unexposed and dengue exposed subjects who will continue in the study but refuse to receive the next CYD dengue vaccine injection(s) will be proposed to be blood sampled for HPV immunogenicity assessment post Gardasil dose 2.

\*\*\*\*: All subjects will either attend an unscheduled visit (V00) or have an unscheduled phone call (PC00) during the study pause and **before** the next scheduled visit (V05, V06 or V07). During the unscheduled visit or phone call, the subject will be informed about the new safety data thanks to a "dear participant letter" and also on their baseline serostatus result. The signature of the ICF/AF by the parents/subjects and the check of contraindications to continue in the study will be at the next visit planned, as applicable.

\*\*\*\*: MA will be delivered to subjects who will not receive further CYD dengue vaccine injection but consent to continue their participation in the study.

††††: The 6-month phone call will be given to all subjects who consented to continue in the study whether they were identified "dengue-exposed" or "dengue unexposed"

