#### **PPG**

The subjects presenting with at least one of the following relevant protocol deviations will be excluded from the PPG:

- Subject did not meet all protocol-specified inclusion criteria or met at least one of the protocol-specified exclusion criteria
- Subjects identified as dengue non-immune subjects (seronegative) at baseline
- Subject is seropositive at baseline for Gardasil (ie, at least one Ab levels against Gardasil HPV antigens > LLOQ at baseline)
- Subject did not complete the Gardasil vaccination schedule (until V05)
- Subject received a vaccine other than the one that she was randomized to receive (until V05 for Group 1, V06 for Group 2)
- Administration of vaccine was not done as per-protocol (site and route of administration) (until V05)
- Subject did not receive vaccine in the proper time window (until V05 for Group 1, V06 for Group 2)
- Subject did not provide after the 2nd dose of Gardasil a post-dose serology sample in the proper time window or a post-dose serology sample was not drawn (V05 for Group 1, V06 for Group 2)

- Subject received a protocol-prohibited medication (prohibited therapies/ medications/ vaccines are indicated in the Protocol Section 6.7) (until V05 for Group 1, V06 for Group 2)
- Subject's serology sample after the 2nd dose of Gardasil did not produce a valid test result, ie, no Gardasil antigen titer available (V05 for Group 1, V06 for Group 2)

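### Three Gardasil per-protocol exclusions run to V05 in Group 1 but V06 in Group 2, so Group 2 children could be removed for events after their HPV endpoint blood

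*SAP*

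**What the plan says.** SAP 5.2.2 lists the deviations that remove a child from the PPG. Three of them end at V05 for Group 1 and at V06 for Group 2:

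- wrong vaccine: "Subject received a vaccine other than the one that she was randomized to receive (until V05 for Group 1, V06 for Group 2";
- dosing window: "Subject did not receive vaccine in the proper time window (until V05 for Group 1, V06 for Group 2";
- medication: "Subject received a protocol-prohibited medication", followed by the same split limit.

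Protocol 12.2.2 has the same split on all three; its window bullet reads "Subject did not receive vaccines in the proper time window (until V05 for Group 1, V06 for Group 2". Two neighbouring SAP bullets end at V05 for everyone: site and route of administration, and schedule completion ("Subject did not complete the Gardasil vaccination schedule (until V05").

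On the endpoint sample, protocol 9.1.1.2 says of the HPV assay: "This assay will be performed on samples taken at V01, V02, and V05". The footnote to SAP Table 3.1 gives the order within a visit: "Blood samples planned during vaccination visits will be taken before vaccination". SAP 5.2.5 makes the PPG the main set for the Gardasil non-inferiority tests, with confirmation on immune subjects in the FAS.

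**The concern.** A per-protocol set should remove subjects for deviations that could distort the endpoint it serves. For the Gardasil comparison that endpoint is fixed once blood is drawn at V05. A criterion that runs on to V06 in one arm only can remove a Group 2 child for something that happened afterwards, although the HPV titer is valid and unaffected.

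Two things are at stake. The main Gardasil analysis set would be selected in one arm on post-endpoint events. And some Group 2 children could be lost when SAP 5.5 makes formal testing of the co-primaries conditional on at least 121 evaluable children per group, a number the plan itself expects may be hard to reach.

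**Working it through.** **Order of events.**

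| | Group 1 | Group 2 |
|---|---|---|
| Gardasil dose 2 | V04 | V04 |
| CYD dose 2 | V04 | V05, after the blood draw |
| HPV endpoint blood | V05 | V05 |
| HPV blood at V06 | no V06 visit | none (dengue antibodies only) |
| Limit of the three criteria | V05 | V06 |

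Sources: SAP Table 3.1, protocol Table 7.1, and protocol 5.1.4, where the Visit 5 blood sample is step 8 and the Group 2 injection is step 11. Group 1's CYD dose 2 precedes its HPV endpoint; Group 2's follows it. The extra Group 2 segment is one injection plus 28 to 42 days (V06 is V05 + 28 days, window +14). Events before the V05 draw under the same criteria can affect the titer and should still count.

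**How a valid sample could be excluded.**

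- *Medication.* Protocol 6.7 prohibits other vaccines within 4 weeks after each trial vaccination. A Group 2 child given another vaccine a week after V05 meets the exclusion; a Group 1 child with the same event is kept.
- *Window.* Group 2's V05 is timed in two ways: V02 + 6 months (+14 days) for CYD dose 2, and V04 + 28 days (+14 days) for the HPV blood. Let V02 be *a* days late (0 to 14) and V04 be *b* days off target (−20 to +20). Both count from V01 + 6 months + 28 days, so the two V05 windows are [*a*, *a*+14] and [*b*, *b*+14]. They share no day when |*a* − *b*| > 14. That holds for 90 combinations with *b* ≤ −15, 105 with *b* from −14 to −1, and 21 with *b* ≥ 15: 216 of 15 × 41 = 615, or 35%. This counts permitted combinations and does not forecast subjects. It shows only that a child can have HPV blood on time and CYD dose 2 off-window.

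**The plan's own power.** For each antigen or serotype, power = Φ(0.301 / (SD·√(1/n₁ + 1/n₂)) − 1.96), with true difference 0 and SDs 0.6, 0.4, 0.5, 0.5 (HPV) and 0.7, 0.7, 0.5, 0.5 (dengue). The product over all eight is:

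- n = 222 per group: 98.9% (plan 98.4%);
- n = 121 per group: 80.8% (plan 80.4%). A noncentral t gives 80.3%.

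The plan's figures are reproduced to within about half a point.

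**Effect of losing Group 2 children from the PPG.** Group 1 is held at 121 and dengue power is held at its value for 121 per group (0.8353). The losses are assumptions, because the documents give no count.

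| Group 2 PPG | HPV power | Global power |
|---|---|---|
| 121 | 0.9676 | 0.8082 |
| 113 (8 lost) | 0.9615 | 0.8031 |
| 109 (about 10% lost) | 0.9579 | 0.8001 |

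The largest drop in global power is 0.8082 − 0.8001 = 0.0081, or 0.8 points.

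**Effect on the 121 threshold.** To keep 121 after a loss *f*, Group 2 needs 121/(1 − *f*) beforehand: 123 at 1%, 125 at 3%, 128 at 5%, 135 at 10%. A loss of 1% to 3% of 121 is about 1 to 4 children.

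**The case against.** The strongest defence is that the limits are symmetric by dose. V05 in Group 1 and V06 in Group 2 each take in Gardasil doses 1 and 2 and CYD doses 1 and 2, with about four weeks after the last of them. Protocol 6.7 also defines prohibited therapies relative to each trial vaccination. This probably explains the label, and it rules out saying that Group 1 is never judged on CYD dose 2: it is, at V04. It does not justify the limit for this endpoint, since only Group 1's dose comes before the HPV blood. CYD deviations also have their own set, the PPC, and the site/route bullet already stops at V05 in both arms.

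The SAP window bullet may not reach CYD dose 2 at all. It says vaccine in the singular where the PPC list uses the plural, and the SAP narrowed schedule completion to Gardasil. If it means Gardasil only, running it to V06 excludes nobody. But the protocol bullet is plural and the SAP does not settle the matter.

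A reader might infer that the 8 children are a known loss of 8/264 = 3.0%. Protocol 5.1.3 does say "all subjects except 8 (all from Group 2) have received the second injection of CYD dengue vaccine", but it also says those 8 were waiting for V05, so their HPV blood was pending too. After a pause of about 2 months they may already fail the separate serology-window bullet, and some may be dengue seronegative and excluded anyway. The fix might recover none of them.

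A reader might also infer that the 121 threshold is in danger. That needs the PPG to be the limiting set. A child with a deviating CYD dose 2 leaves the PPC as well, and the PPC further requires dose 3 and the V08 blood. The documents do not show which set is smaller. Finally, the FAS confirmation does not apply these exclusions and limits the harm.

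**Conclusion.** As written, the three criteria could exclude Group 2 children from the main Gardasil analysis for events after a valid endpoint sample, with no matching post-endpoint period in Group 1. That follows from the visit order alone and rests on no assumption, except that the window bullet matters only if it covers CYD dose 2.

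The size is not in the documents and is probably small, since all but 8 children had CYD dose 2 before the amendment was written. The 1% to 10% losses used above are assumptions. Under the plan's SDs and margin, even the 10% case costs under 1 point of power. The documents do not support claims that comparability is in fact broken, that a stated number of children is lost, or that formal testing will be prevented. Nor do they indicate a direction of bias. The point is worth correcting because it concerns the main analysis set and the correction is nearly free.

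**What to change.** In the three bullets of SAP 5.2.2 (PPG), and the same three in protocol 12.2.2, replace the split visit limit with *(until the V05 blood sample, both groups)*. State that deviations at or after the V05 CYD injection are handled in the PPC. In the same edit, change V06 to V05 for Group 2 in the two bullets on the post-dose-2 serology sample and its valid result, because no HPV sample exists at V06. State whether the window bullet covers Gardasil only or both vaccines. The sponsor should also reconcile the two timings given for Group 2's V05.

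The cost is a wording change, an entry in SAP 5.7 and one date cut-off in the deviation program. No planned sample size or power figure changes. There is one downside to state openly: a CYD dose 2 deviation would then exclude a child from the PPG only in Group 1. That is defensible because only there does the dose precede the endpoint.

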#### **PPC**

The subjects presenting with at least one of the following relevant protocol deviations will be excluded from the PPC:

- Subject did not meet all protocol-specified inclusion criteria or met at least one of the protocol-specified exclusion criteria
- Subjects identified as dengue non-immune subjects (seronegative) at baseline
- Subject did not complete the vaccination schedule
- Subject received a vaccine other than the one that she was randomized to receive
- Administration of vaccines was not done as per-protocol (site and route of administration)
- Subject did not receive vaccines in the proper time window
- Subject did not provide after the 3rd dose of CYD dengue vaccine a post-dose serology sample in the proper time window or a post-dose serology sample was not drawn (V08, M13 for Group 1 and M14 for Group 2)
- Subject received a protocol-prohibited medication (prohibited therapies/ medications/ vaccines are indicated in the protocol Section 6.7) (until V07)
- Subject's serology sample did not produce a valid test result, ie, no Neutralizing Ab titers against any of the four parental dengue virus serotypes of CYD dengue vaccine available (at V08, M13 for Group 1 and M14 for Group 2)

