- 2) Have the subject and/or the subject's parent (s)/legally acceptable representative(s), date and sign the new AF and/or ICF version, as applicable

Phone Call 6 (PC6) for Group 1 (Month 9 [Month 7 + 2 months]; 2 months [+8 days] after Visit 5) or Group 2 (Month 10 [Month 8 + 2 months]; 2 months [+8 days] after Visit 6)

The same procedures as those described for PC1 will be followed.

Visit 7 (Month 12 (Group 1) or Month 13 (Group 2); 12 or13 months [± 10 days] after Visit 1)

For subjects who will return at V07 after the suspension of vaccination

- Present the changes brought to the study design to the subject/subject's parent (s)/legally
 acceptable representative(s) in more detail, answer any of his/her/their questions, and ensure
 that he/she/they has/have been informed of all aspects that are relevant to their decision to
 continue participating in the study
- 2) Have the subject and/or the subject's parent (s)/legally acceptable representative(s), date and sign the new AF and/or ICF version, as applicable

The same procedures as those described for Visit 4 will be followed, except that no dose of Gardasil will be injected and the CYD dengue vaccine will be injected to all eligible subjects (third and last dose given 6 months post-dose 2).

Phone Call 7 (PC7) (Month 12 + 7 days [Group 1] or Month 13 + 7 days [Group 2]; 7 days [+8 days] after Visit 7)

The same procedures as those descried for PC1 will be followed.

Visit 8 (Month 13 (Group 1) or Month 14 (Group 2); 28 [+14] days after Visit 7)

The Investigator or designated study personnel will:

- 1) Review the pages of the DC with the parent/legally acceptable representative, including any AEs, medications, or therapy that occurred since vaccination.
- 2) Perform a physical examination and record the subject's axillary temperature.
- 3) Check concomitant medications and record every reportable medication ongoing at the time of vaccination.
- 4) Obtain a blood sample (see Section 7.1 for detailed instructions regarding the handling of blood samples).
- 5) Give the parent/legally acceptable representative a memory aid (MA).
- 6) Remind the parent/legally acceptable representative to keep the MA available when they will be called for Safety Follow-up Telephone Call at a specified date and time.
- 7) Complete the relevant CRF pages for this visit.
- 8) Complete the termination record of the CRF.

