6.7 Concomitant Medications and Other Therapies

At the time of enrollment, ongoing medications including other therapies e.g., blood products, should be recorded in the source document as well as new medications prescribed for new medical conditions/AEs during trial participation.

Documentation in the CRF of concomitant medication will be limited to specific categories of medication of interest beginning on the day of vaccination. This may include medications of interest that were started prior to the day of vaccination.

Reportable medications will be collected in the CRF from the day of vaccination to the end of the solicited and unsolicited follow-up period (e.g., 28 day safety follow-up) as they may impact the response to the vaccination and impact the consistency of the information collected on concomitant medications at any vaccination.

The "reportable" medications are distributed according to two categories:

- Category 1 (Restricted therapies) antipyretics, analgesics, non-steroidal anti-inflammatory drugs (NSAIDs), corticosteroids, and other immune modulators *Note: inhaled and topical steroids should not be captured*
- Category 2 (Prohibited therapies for the PP):
 - Vaccines (other than the trial vaccines) in the 4 weeks before and after each trial vaccination
 - Immunosuppressive therapy such as anti-cancer chemotherapy or radiation therapy or long-term systemic corticosteroids (for more than 2 consecutive weeks) in the 4 weeks after each trial vaccination
 - Immune globulins, blood or blood-derived products in the 4 weeks before and after each trial vaccination
- The information reported in the CRF for each reported medication will be limited to:
- Trade name
- Given as treatment or as prophylaxis
- Medication category
- Start and stop dates

Dosage and administration route will not be recorded. Homeopathic medication will not be recorded. Topical treatment will not be recorded.

The fact that a medication was given in response to an AE will be captured in the "Action Taken" column of the AE only. No details will be recorded in the concomitant medication module of the CRF unless the medication received belongs to one of the prelisted categories. Medications will not be coded.

7 Management of Samples

Blood samples for the assessment of antibody responses will be collected at Visits 1, 2, 3, 5, 6, and 8. See the Table of Study Procedures and Section 5.1.3 for details of the sampling schedule.

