- Subject received a protocol-prohibited medication (prohibited therapies / medications / vaccines are indicated in Section 6.7) (until V07)
- Subject's serology sample did not produce a valid test result, i.e., no Neutralizing Ab titers against any of the four parental dengue virus serotypes of the CYD dengue vaccine available (at V08, M13 for Group 1 and M14 for Group 2)

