#### **Individual hypotheses on CYD response for each antigen:**

A non-inferiority testing approach will be used to compare GMTs 28 days after the third injection of CYD dengue vaccine between groups for each serotype “i” based on the following individual hypotheses:

$$H_0^i: \text{GMT}_{\text{Group1}}^i / \text{GMT}_{\text{Group2}}^i \leq \frac{1}{\delta} \Leftrightarrow \log_{10}(\text{GMT}_{\text{Group1}}^i) - \log_{10}(\text{GMT}_{\text{Group2}}^i) \leq -\log_{10}(\delta)$$

$$H_1^i: \frac{1}{\delta} < \text{GMT}_{\text{Group1}}^i / \text{GMT}_{\text{Group2}}^i > \frac{1}{\delta} \Leftrightarrow \log_{10}(\text{GMT}_{\text{Group1}}^i) - \log_{10}(\text{GMT}_{\text{Group2}}^i) > -\log_{10}(\delta)$$

with:

i, serotypes in {1, 2, 3, 4}

$\delta$  non-inferiority limit is set at 2 ie, 0.301 ( $=\log_{10}[2]$ ), for each serotype “i”

Non-inferiority for serotype i will be demonstrated if the lower bound of the 2-sided 95% CI is greater than  $-\delta$ .

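### Read literally, the PPC prohibited-therapy exclusion stops at the third CYD dose and omits the four weeks after it, the window nearest the co-primary titre

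*SAP*

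**What the plan says.** The third CYD dose is given at V07, described in protocol 5.1.4 as the "third and last dose given 6 months post-dose 2". The dengue sample follows at "Visit 8 (Month 13 (Group 1) or Month 14 (Group 2); 28 [+14] days after Visit 7". SAP 5.1.1.1 tests the CYD co-primary hypothesis on that sample; the aim is to "compare GMTs 28 days after the third injection of CYD dengue vaccine between groups". SAP 5.2.5 makes the PPC the main set for this test, with confirmation on the dengue-immune subjects of the FAS.

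Protocol 6.7 lists Category 2 therapies as prohibited for the per-protocol analysis and gives each its own window. Other vaccines count in the four weeks before and after each trial vaccination. Immunosuppressive therapy counts in the four weeks after. The third item reads "Immune globulins, blood or blood-derived products in the 4 weeks before and after each trial vaccination". The PPC bullet that applies this list ends at V07 in the SAP: "Subject received a protocol-prohibited medication (prohibited therapies/ medications/ vaccines are indicated in the protocol Section 6.7) (until V07". The protocol has the same limit: "Subject received a protocol-prohibited medication (prohibited therapies / medications / vaccines are indicated in Section 6.7) (until V07". The two documents agree, so this is not a SAP departure from the protocol.

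**The concern.** The limit falls on the day of the dose whose response is the endpoint. Taken at its word, it removes a subject who received immune globulin in the four weeks after dose 1, about a year before V08. It keeps a subject who received the same product two weeks before V08. Blood products can add antibody passively, and immunosuppressants or another vaccine can alter the response being measured. Protocol 6.7 itself gives possible influence on the vaccine response as a reason for recording these medications.

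At stake is the membership of the main analysis set for one co-primary objective. Two programmers could build different PPCs from the same sentence.

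**Working it through.** **Windows against the limit.** Dose visits come from the Table of Study Procedures, the four-week windows from protocol 6.7, and the limit from the PPC bullet.

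| CYD dose | Visit, Group 1 / Group 2 | Four weeks after the dose | Inside the literal limit? |
|---|---|---|---|
| 1 | V01 / V02 | before V07 | yes |
| 2 | V04 / V05 | before V07 | yes |
| 3 | V07 / V07 | after V07 | no |

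The four weeks before dose 3 precede V07 and are covered. The uncovered interval from V07 to the sample is 28 to 42 days. Section 6.7 prohibits the therapies in the first 28 of these, and the CRF collects medication for days 0 to 28 after each injection (footnote to SAP Table 3.1). Days 29 to 42 of a late V08 are neither prohibited nor collected.

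**Other PPC bullets.** The bullet on receiving a vaccine other than the randomized one most naturally concerns the allocated trial vaccine. Exclusion criterion 3 concerns vaccines planned at enrolment. Neither reaches immune globulins, blood products or immunosuppressants newly given after V07.

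**Size of the effect.** The documents give no rate, so these are assumptions.
- If 1% to 5% of subjects receive a Category 2 therapy in the four weeks after dose 3: 0.01 × 121 = 1.2 and 0.05 × 121 = 6.1 subjects per group.
- Two such subjects in one group only, each shifted by 1 log10: 2/121 = 0.0165 log10, and 0.0165/0.301 = 5.5% of the margin.
- Six such subjects in one group only: 6/121 = 0.0496 log10, or 16.5% of the margin.
- Equal numbers and equal shifts in both groups: no movement in the difference.

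**Power near the testing threshold.** Inputs from SAP 5.5: margin 0.301, one-sided alpha 0.025, true difference 0, SDs 0.6, 0.4, 0.5 and 0.5 (HPV) and 0.7, 0.7, 0.5 and 0.5 (dengue). For each endpoint, with df = 2n − 2,

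power = 1 − F(t₀.₉₇₅; df, 0.301/(SD·√(2/n))),

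where F is the noncentral t distribution function and t₀.₉₇₅ is the central t quantile on the same df. The eight powers are multiplied.
- At n = 121: 97.3% (SD 0.6), above 99.9% (0.4), 99.7% (0.5, four endpoints) and 91.5% (0.7, two endpoints). The product is 80.3%, against the stated 80.4%. The plan's figure is reproduced to within rounding.
- At n = 120, 119 and 118 for all eight endpoints: 79.8%, 79.2% and 78.7%.
- The correction touches only the PPC. With dengue at 120 and HPV kept at 121: 0.8269 × (0.8032/0.8312) = 79.9%.
- A normal approximation gives 80.8% at 121 and 80.3% at 120. So crossing 80% at exactly 120 depends on the method, but 120 fails the plan's stated minimum of 121 in any case.

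**The case against.** The best defence is that the bullet refers the reader to Section 6.7, whose windows attach to each trial vaccination, and V07 is the last vaccination visit. On that reading the limit means all windows belonging to doses through V07, the four weeks after it included, and there is no gap. This is possible, but it is not stated. It also sits poorly with the matching bullet for the Gardasil set (PPG), which ends at V05 for Group 1 and V06 for Group 2. Neither group receives an injection at its visit, so those labels look like time points rather than dose labels.

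A reader might go further and infer that the two per-protocol sets follow opposite logic. The documents do not support that. The HPV sample is drawn at V05 in both groups, so the V06 label for Group 2 does not mark its endpoint sample, and the PPG labels are not a reliable guide to a design rule.

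It is also fair that planned vaccination within four weeks of a trial dose was an exclusion criterion, which should reduce the commonest kind of exposure. At V07 both groups receive CYD alone, so the dose-3 regimen gives no reason for exposure to differ by group. Both points stand. They reduce the likely effect but do not supply the missing words.

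**Conclusion.** The point holds as a minor correction. On a literal reading, the PPC omits the post-dose-3 window that the protocol's own Section 6.7 treats as prohibited for the per-protocol analysis, and no other PPC rule clearly restores it. The intended meaning may be wider than the text.

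Two stronger conclusions are tempting and should not be drawn. One is that the co-primary comparison is materially biased. The documents give no frequency of such therapies. Under the assumed one-sided case of two subjects the shift is about 0.017 log10 against 0.301, and even six subjects all in one group give about 0.050. The other is that naming V08 as the limit would cover everything up to the sample. It would not, because Section 6.7 and CRF collection both end at day 28.

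**What to change.** In the PPC bullet of SAP 5.2.2, replace the V07 limit with wording that applies the Section 6.7 windows to all trial vaccinations, the third CYD dose included: that is, up to 28 days after V07, or up to the V08 sample if that comes earlier. Record the change in SAP 5.7. Make the same change to protocol 12.2.2 at its next amendment; protocol 5.3 requires amendments to be written and notified or approved, so a separate amendment for this alone is not warranted. State openly that days 29 to 42 of a late V08 remain uncovered.

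No new data are needed for the 28 days. The cost is that a few subjects may leave the PPC. If the evaluable count is close to 121 per group, this could turn planned non-inferiority testing into a descriptive analysis, so the rule should be fixed before that count is known.
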